Anesthesia	Principal Anesthesia Technique Epidural General Local Monitored Anesthesia care (MAC) / IV Sedation None Regional Spinal Other Unknown	Cohort characteristics
SBP	Systolic blood pressure with time stamp	Potential predictors: univariate vs. multivariate time series; clinician-defined

		predictor variables.
MAP	Mean arterial blood pressure with time stamp	Potential predictors: univariate vs. multivariate time series; clinician-defined predictor variables.
HR	Heart rate/pulse rate with time stamp	Potential predictors: univariate vs. multivariate time series; clinician-defined predictor variables.
RR	Respiratory rate with time stamp	Potential predictors: univariate vs. multivariate time series; clinician-defined predictor variables.
SpO2	Oxygen saturation by pulse oximetry with time stamp	Potential predictors: univariate vs. multivariate time series; clinician-defined predictor variables.
Intraoperative Phenylephrine (>200 mcg)	1/0 Yes/No	Potential predictor Potential confounder
Intraoperative Ephedrine (>10 mg)	1/0 Yes/No	Potential predictor Potential confounder
Intraoperative Norepinephrine	1/0 Yes/No	Potential predictor Potential confounder
Intraoperative Vasopressin	1/0 Yes/No	Potential predictor Potential confounder
Intraoperative Epinephrine	1/0 Yes/No	Potential predictor Potential confounder
Intraoperative Dobutamine	1/0 Yes/No	Potential predictor Potential confounder
Intraoperative Milrinone	1/0 Yes/No	Potential predictor Potential confounder
Time of patient entering room	Time/date	To identify preoperative vitals

Time of patient leaving room	Time/date	To identify postoperative vitals
------------------------------	-----------	----------------------------------

Source: Cerner extraction (please see appendix for details of the CIHI codes)

Variable name	Legend/ICD-10 code	Reason for request
IDN	ID (deidentified)	To deidentify patients in the dataset
MRN	ID	Required for manual chart review of variables that cannot be extracted automatically
Age	Age	Cohort characteristics
Gender	Male vs. Female	Cohort characteristics
Surgical priority	E0: STAT E1: <1 hour E2: <4 hours E2OB: <2 hours E3: <8 - 12 hours E4: <48 hours Elective A dichotomized variable of emergent/urgent vs. elective will be created as a predictor in the primary model	Cohort characteristics
Procedure_code	Cerner procedure code	Cohort characteristics
Procedure_text	The corresponding free text to the Cerner procedure code	Cohort characteristics
ASA	American Society of Anesthesia Physical Classification Score Score from 1 - 6 assessed by consulting anesthesiologist	Cohort characteristics

SBP	Systolic blood pressure with time stamp (day of surgery to POD3)	Potential predictors: univariate vs. multivariate time series; clinician-defined predictor variables.
MAP	Mean arterial blood pressure with time stamp (day of surgery to POD3)	Potential predictors: univariate vs. multivariate time series; clinician-defined predictor variables.
HR	Heart rate/pulse rate with time stamp (day of surgery to POD3)	Potential predictors: univariate vs. multivariate time series; clinician-defined predictor variables.
RR	Respiratory rate with time stamp (day of surgery to POD3)	Potential predictors: univariate vs. multivariate time series; clinician-defined predictor variables.
SpO2	Oxygen saturation by pulse oximetry with time stamp (day of surgery to POD3)	Potential predictors: univariate vs. multivariate time series; clinician-defined predictor variables.
RCRI	Revised cardiac risk index total score	Potential predictor of MINS
CCI	Charlson comorbidity index total score	Potential predictor of MINS
CVA	Presence of cerebrovascular disease CIHI preoperative diagnoses: G45.x, G46.x, H34.0, I60.x– I69.x 1/0 Yes/No	Potential predictor RCRI, CCI
IHD	Presence of ischemic heart disease CIHI preoperative diagnoses: I20.x, I21.x, I22.x, I24.x, I23.x, I25.x, Z95.1, Z95.5 1/0 Yes/No	Potential predictor RCRI, CCI

CHF	History of congestive heart failure CIHI preoperative diagnoses: I09.9, I11.0, I13.0, I13.2, I25.5, I42.0, I42.5–I42.9, I43.x, I50.x, P29.0 1/0 Yes/No	Potential predictor RCRI, CCI
Preoperative creatinine	Value in $\mu\text{mol}/\text{L}$	Potential predictor RCRI
Insulin use	Insulin (medium or long-acting) from medical administrative record 1/0 Yes/No	Potential predictor RCRI
CKD	CKD stage 4-5 or dialysis dependednt CIHI preoperative diagnoses: N18.3, N18.4, N18.5, Z49.0– Z49.2, Z99.2 1/0 Yes/No	Cohort demographics Potential predictor RCRI, CCI
PVD	Presence of peripheral vascular disease CIHI preoperative diagnoses: I70-I79 1/0 Yes/No	Potential predictor of MINS, CCI
Dementia	History of dementia CIHI preoperative diagnoses: F00.x-F03.x, F05.1, G30.x, G31.1 1/0 Yes/No	Potential predictor CCI
Chronic pulmonary disease	History of chronic pulmonary disease CIHI preoperative diagnoses: I27.8, I27.9, J40.x–J47.x, J60.x– J67.x, J68.4, J70.1, J70.3 1/0	Potential predictor CCI

	Yes/No	
Connective tissue/rheumatic disease	
History of connective tissue or rheumatic disease
 
CIHI preoperative diagnoses: M05.x, M06.x, M31.5, M32.x- M34.x, M35.1, M35.3, M36.0
 
1/0
 
Yes/No
	Potential predictor CCI
Peptic ulcer disease	
History of peptic ulcer disease
 
CIHI preoperative diagnoses: K25.x-K28.x
 
1/0
 
Yes/No
	Potential predictor CCI
Mild liver disease	
History of mild liver disease
 
CIHI preoperative diagnoses: B18.x, K70.0-K70.3, K70.9, K71.3-K71.5, K71.7, K73.x, K74.x, K76.0, K76.2-K76.4, K76.8, K76.9, Z94.4
 
1/0
 
Yes/No
	Potential predictor CCI
Severe liver disease	
History of moderate - severe liver disease
 
CIHI preoperative diagnoses: I85.0, I85.9, I86.4, I98.2, K70.4, K71.1, K72.1, K72.9, K76.5, K76.6, K76.7
 
1/0
 
Yes/No
	Potential predictor CCI
Diabetes uncomplicated	
History of diabetes without chronic complications
 
CIHI preoperative diagnoses: E10.0, E10.1, E10.6, E10.8, E10.9, E11.0, E11.1, E11.6, E11.8, E11.9, E12.0, E12.1, E12.6, E12.8, E12.9, E13.0, E13.1, E13.6, E13.8, E13.9, E14.0, E14.1, E14.6, E14.8, E14.9
 
1/0
	Potential predictor CCI

	Yes/No	
Diabetes complicated	
History of diabetes with chronic complications
 
CIHI preoperative diagnoses: E10.2-E10.5, E10.7, E11.2-E11.5, E11.7, E12.2-E12.5, E12.7, E13.2-E13.5, E13.7, E14.2-E14.5, E14.7
 
1/0
 
Yes/No
	Potential predictor CCI
Hemiplegia/paraplegia	
History of hemiplegia or paraplegia
 
CIHI preoperative diagnoses: G04.1, G11.4, G80.1, G80.2, G81.x, G82.x, G83.0-G83.4, G83.9
 
1/0
 
Yes/No
	Potential predictor CCI
Localized malignancy	
History of malignancy (including lymphoma and leukemia, except malignant neoplasm of skin)
 
CIHI preoperative diagnoses: C00.x-C26.x, C30.x-C34.x, C37.x-C41.x, C43.x, C45.x-C58.x, C60.x-C76.x, C81.x-C85.x, C88.x, C90.x-C97.x
 
1/0
 
Yes/No
	Potential predictor CCI
Metastatic tumour	
History of metastatic solid tumour
 
CIHI preoperative diagnoses: C77.x-C80.x
 
1/0
 
Yes/No
	Potential predictor CCI
AIDS/HIV	
History of acquired immunodeficiency syndrome or human immunodeficiency virus
 
CIHI preoperative diagnoses: B20.x-B22.x, B24.x
 
1/0
	Potential predictor CCI

	Yes/No	
Hypertension	Presence of hypertension CIHI preoperative diagnoses: I10-I15 1/0 Yes/No	Cohort demographics
PE	Presence of pulmonary embolism within MINS window CIHI postoperative diagnoses: I26 1/0 Yes/No	MINS diagnosis criteria
Atrial fibrillation	Presence of atrial fibrillation within MINS window CIHI postoperative diagnoses: I48.x 1/0 Yes/No	MINS diagnosis criteria
Cardioversion	Cardioversion within 24 hours MINS 1/0 Yes/No	MINS diagnosis criteria
Sepsis	Presence of sepsis within MINS window CIHI postoperative diagnoses: R57.2 1/0 Yes/No	MINS diagnosis criteria
MINS	Based on MINS diagnostic criteria as described (primary outcome) 1/0 Yes/No	MINS diagnosis criteria
MIpost	Diagnosis of myocardial infarction postoperatively 1/0 Yes/No	Third Universal Definition or per cardiology note

PMI	Diagnosis of postoperative myocardial injury postoperatively 1/0 Yes/No	StEP criteria
Troponin	Preoperative and postoperative HS troponin values with time stamps Value in ng/L	MINS diagnosis criteria Time of MINS diagnosis Exclusion Criteria Patients who had positive troponin on postoperative day 4 will be excluded, since vital signs are only included up to postoperative day 3 for consistency.
Estimated blood loss	Intraoperative recorded blood loss Volume in mL	Potential predictor
Surgical Service	Vascular General Orthopedics ENT Gynecology Plastics Other	Potential predictor
High risk surgery	Suprainguinal vascular, intrathoracic, intraperitoneal 1/0 Yes/No	Potential predictor RCRI
Disposition postoperatively	Ward vs HAU vs ICU	Cohort Characteristic
HAU admission start time	Time stamp	Determine setting of vital measurement
HAU admission end time	Time stamp	Determine setting of vital measurement
ICU admission start time	Time stamp	Determine setting of vital measurement

ICU admission end time	Time stamp	Determine setting of vital measurement
Preoperative NT-proBNP	Value in ng/L	Potential predictor
Preoperative Hemoglobin	Value in g/L	Cohort characteristics Potential predictor
Preoperative GFR	Value in mL/min	Cohort characteristics Potential predictor
Preoperative beta blocker use	Preoperative use (metoprolol, bisoprolol, carvedilol, atenolol, propranolol, labetalol, nadolol) 1/0 Yes/No	Potential predictor Potential confounder Note that in order to obtain these variables and due to the limited analytic time from the Cerner team, all medications in the patient's medication administration record that is noted as completed were pulled
Preoperative ACEI/ARB	Preoperative use (captopril, enalapril, ramipril, perindopril, lisinopril, candesartan, irbesartan, losartan, telmisartan, valsartan, sacubitril/valsartan) 1/0 Yes/No	Potential predictor Potential confounder Note that in order to obtain these variables and due to the limited analytic time from the Cerner team, all medications in the patient's medication administration record that is noted as completed were pulled
Postoperative Phenylephrine (>200mcg)	1/0 Yes/No	Potential predictor Potential confounder
Postoperative Ephedrine (>10mg)	1/0 Yes/No	Potential predictor Potential confounder

Postoperative Norepinephrine	1/0 Yes/No	Potential predictor Potential confounder
Postoperative Vasopressin	1/0 Yes/No	Potential predictor Potential confounder
Postoperative Epinephrine	1/0 Yes/No	Potential predictor Potential confounder
Postoperative Dobutamine	1/0 Yes/No	Potential predictor Potential confounder
Postoperative Milrinone	1/0 Yes/No	Potential predictor Potential confounder
In hospital mortality	1/0 Yes/No	Outcome Cohort characteristic
Start of surgery (time/date) [Enters OR]	Time/date	To define the start of the time series
End of surgery (time/date) [Leaves OR]	Time/date	To define the start of the postoperative time series
Length of OR	Duration in minutes	Potential predictor
PACU length of stay	Duration in minutes (if available, otherwise calculated based on the following two values)	Potential Predictor
Time of PACU admission	Time/date	For time stamps
Time of PACU discharge	Time/date	For time stamps
Time/date of hospital discharge	Time/date	To verify inclusion criteria
Readmission within 3 days of surgery	1/0 Yes/No	Patients who underwent repeat surgery or were readmitted within the first 72 hours postoperatively will be excluded.
Repeat surgery within 3	1/0	Patients who underwent

days of surgery	Yes/No	repeat surgery or were readmitted within the first 72 hours postoperatively will be excluded.
-----------------	--------	---

CIHI – Canadian Institute for Health Information, ICD-10 (International statistical classification of diseases and related problems) codes

References:

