Following research ethics board approval, data will be extracted from Cerner Surginet Anesthesia (intraoperative electronic records) and Cerner PowerChart (preoperative and postoperative electronic records). The extracted data will consist of cohort characteristics (patient, anesthetic, surgical variables relevant to MINS (see Data Dictionary below), and patient vital signs with time stamps up to postoperative day 3. The time series time stamps will be transposed to have the start of surgery as 00:00, Jan 1, 2020. A manual chart review will also be performed to extract data not automatically retrieved from Cerner and Surginet (e.g. diagnoses of morbidities). We will extract relevant preoperative comorbidities, including RCRI and Charlson Comorbidity Index categories that are available to the Cerner team via CIHI with no date limit to obtain all preoperative comorbidities (please see Appendix). The Cerner, Surginet, and chart review data will then be linked by de-identified study ID and full surgery date.

Duration of data collection

Preoperative laboratory values are collected within 30 days before surgery. Preoperative vitals are collected within 24 hours before surgery. The total duration of subsequent data collection will be from the time of surgery up to postoperative day 3 (since the MINS protocol monitors for 3 days) or hospital discharge or death, whichever occurs first. Since 90% of MINS happen between postoperative days zero and two (4) and the frequency of monitoring would likely decrease by postoperative day 3, we will model troponin from postoperative day 0 to postoperative day 2 for the primary analysis to balance utility of the temporal model and prediction data quality.

Outcome

In the primary model, we will model high-sensitivity troponin (hsTnT) level as a continuous outcome, such that the model will remain useful if the troponin threshold definitions for MINS evolve.

In the secondary model, we will use the American Heart Association (AHA) definitions (6) for MINS, briefly:

1. Postoperative hsTnT 20 to <65 ng/L with an absolute increase of ≥ 5 ng/L amongst any postoperative troponins, or ≥ 65 ng/L, “attributable to a presumed ischemic mechanism (ie, supply-demand mismatch or atherothrombosis) in the absence of an overt precipitating nonischemic cause (eg, pulmonary embolism)”. The timestamp for laboratory diagnosis will be set at the time that the sample of elevated troponin was drawn.

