For generalizability and to decrease bias, we will select features that are routinely collected. Non-vital sign candidate features include age, sex, urgent/emergent procedure (for the index surgery), postoperative GFR, and comorbidities within the RCRI categories.

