***A priori* features in the primary model**

This *a priori* list of predictors will be used for the primary modeling in Objective 1: duration hypotension (summarized as a percentage of duration of MAP<75 mmHg in the duration of time modeled, e.g. postoperative day 0, 1, and 2), age, sex, emergency surgery, RCRI, and postoperative GFR, as well as the postoperative day and the interaction between postoperative day and % duration MAP<75mmHg as detailed below.

Statistical analysis

Missing data

We will exclude patients with no intraoperative or postoperative vital signs and no troponin measurements from the cohort. Complete case analysis will be performed for vital sign features, with each complete case defined as a patient with ≥ 1 vital sign measurement(s) and ≥ 1 troponin measurement(s). Since the frequencies of measurements are different, missing vital signs are not considered missing values for inclusion/exclusion purposes as long as patients meet the complete case criteria. No imputation will be performed for vital sign data.

For features that are not vital signs (e.g. age, sex), we anticipate minimal missing data (as these variables are routinely collected), and assume missing at random. Due to the longitudinal data structure with correlated observations, we opted for a simpler method of imputation for the primary analysis. For features missing $< 1\%$, complete case analysis will be

performed; between 1-<10%, multiple imputation; above 10%, the feature would be excluded from the model and the reason for missing data will be investigated.

Data quality

The data quality of the CIHI vs. chart review results of the comorbidity information will be assessed by Pearson correlation, with chart review as the gold standard.

Cohort characteristics

Continuous data will be presented in mean (SD) if normal, and median (IQR) if non-normally distributed. Categorical data will be presented as frequency (%). The following characteristics will be presented as overall group, and stratified by MINS vs. no MINS:

- Age
- Gender
- American Society of Anesthesiologists' physical status classification (ASA)
- Type of anesthesia (general, neuraxial, peripheral, and/or sedation)
- RCRI score and categories: pre-existing TIA/CVA, insulin dependent diabetes, serum creatinine >177 mmol/L, coronary artery disease, congestive heart failure, and high risk surgery including intrathoracic, intraabdominal or suprainguinal vascular surgery

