- Charlson Comorbidity Index (CCI) score and categories: history of MI, CHF, PVD, CVA/TIA, dementia, chronic pulmonary disease, connective tissue/rheumatic disease, peptic ulcer disease, liver disease, diabetes mellitus, hemiplegia/paraplegia, moderate to severe CKD, local/metastatic malignancy, AIDS/HIV
- Surgical service
- Duration of surgery
- Surgical priority: emergent/urgent vs. elective
- ICU admission preoperatively
- Cardiovascular medications preoperatively: Angiotensin II receptor blockers (ARBs), angiotensin-converting enzyme (ACE) inhibitor, and beta blockers (based on available names extracted from Cerner; may be missing medications that have been held and not restarted in hospital).
- Estimated blood loss
- Use of intraoperative/postoperative vasopressors/inotropes
Yes/no (received anything at all)
Small amount of intraoperative use (phenylephrine (<200 mcg) or ephedrine (<10 mg))
Significant only (i.e. exclude if small doses of phenylephrine (<200 mcg) or ephedrine (<10 mg))
- Laboratory preoperatively (30 days before surgery): NT-proBNP, hemoglobin, creatinine/GFR, troponin
- Respiratory rate
- Postoperative disposition (ward vs. HAU vs. ICU) - multiple entries possible; time of moving in/out of each unit
- Descriptive statistics of troponin as a continuous variable by postoperative days

- Diagnosis of myocardial infarction, MINS, and postoperative myocardial injury
- MINS troponin monitoring
 - o Duration (operative day to the last day of troponin measurement)
 - o Numbers of troponin testing done and frequency
 - o Time of MINS diagnosis (rule in vs. rule out), hours after end of operation as defined by the event of patient leaves the operating room
- Non-MINS causes of troponin elevation
 - o PE/DVT
 - o Sepsis
 - o Rapid atrial fibrillation
 - o Cardioversion < 24 hours
 - o Chronic elevation (excluded)
- Vitals monitoring
 - o Frequency (plot frequency vs. POD)
 - o Duration within POD3
- 30 Day in-hospital mortality

Also, descriptive summaries of the vital statistics as listed in Table 4 will be presented.

Data processing

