The primary analysis will involve building a linear mixed effects model (with random intercepts) to predict the maximum daily troponin level between postoperative days 0 to 2 as the continuous outcome. The postoperative days 0, 1, and 2 accounts for approximately 40%, 40%, and 10% of MINS, respectively (4). Due to the limitations in retrospective data and the daily troponin monitoring, we will use day as a unit for time rather than hour to avoid overestimation of precision by readers.

For the primary and secondary models described in Objectives 1 and 2, an *a priori* list of predictors will be used: duration hypotension (summarized as a percentage of duration of MAP<75 mmHg in the duration of time modeled, e.g. postoperative day 1) age, sex, emergency surgery, RCRI, and postoperative GFR, as well as the postoperative day and the interaction between postoperative day and % duration MAP<75 mmHg as detailed below.

For longitudinal modeling, the vital signs data and troponin data will be aggregated to the day level, so that the model can predict at the daily temporal level. If there are multiple troponin measurements on the same day, the maximum will be taken. This aggregation of the data is necessary to account for the fact that the vital signs and troponin measurements are measured at irregular intervals (both across patients and data types), often due to the acting physician's response to the patient's condition. Additionally, due to this characteristic of the raw data, the vital signs predictors will be created such that they are standardized to be robust to the number of daily measurements performed (for example, by taking the percentage of day duration, NOT the total duration, of blood pressure below a specific threshold across all measurements during that day). A categorical time variable (representing the day of the measurement) will be included as a predictor within the model.

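### Postoperative GFR is a fixed predictor in the primary model, but its source is unstated and no rule makes it precede the troponin it predicts

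*Combined protocol and SAP*

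**What the plan says.** Three sections name postoperative GFR as a model input. Other candidate features lists "urgent/emergent procedure (for the index surgery), postoperative GFR, and comorbidities within the RCRI categories". A priori features in the primary model repeats it for Objective 1: "age, sex, emergency surgery, RCRI, and postoperative GFR, as well as the postoperative day". Primary Modeling repeats it for Objectives 1 and 2: "age, sex, emergency surgery, RCRI, and postoperative GFR, as well as the postoperative day and the interaction". None says which postoperative value is meant (first, lowest, daily or last) or when it must be drawn.

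The sections describing the data name only preoperative renal values. The Cerner part of the Data Dictionary has rows for "Preoperative creatinine" and "Preoperative GFR" and no postoperative counterpart. Cohort characteristics has "Laboratory preoperatively (30 days before surgery): NT-proBNP, hemoglobin, creatinine/GFR, troponin". Duration of data collection states "Preoperative laboratory values are collected within 30 days before surgery", followed by a general window: "The total duration of subsequent data collection will be from the time of surgery up to postoperative day 3", or to discharge or death if earlier.

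The primary outcome is the highest troponin on each of postoperative days 0, 1 and 2. Data processing truncates differently by outcome. For continuous troponin, it cuts the vital sign series at the final troponin in the first three days. For binary MINS, it cuts the data, without limiting this to vital signs, at the diagnostic troponin (or at day 3, discharge or death, if earlier).

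**The concern.** A predictor fixed in advance should be traceable to a data source and should be known before the outcome it predicts. Neither is secured for this term.

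Without a named source, whoever assembles the dataset must decide which renal value to use after the plan is fixed. Without a time rule, that value may come from after the troponin. Table 3 lists acute kidney injury as a postoperative factor associated with MINS or major myocardial complications, so a late GFR could plausibly carry information about an outcome that has already happened. The study's purpose is temporal prediction, and a model that relies on later values cannot be used as evaluated.

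The planned validation would not reveal the problem. Patient-based cross-validation keeps one patient's records out of both training and validation sets at once. It does not check the order of predictor and outcome within a patient, and held-out patients would carry the same late value.

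**Working it through.** The plan gives no figure to reproduce for this point. The check sets the sections side by side and then counts exposure.

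**1. Source.**

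| Section | Renal value named |
|---|---|
| Other candidate features | Postoperative GFR |
| A priori features in the primary model | Postoperative GFR |
| Primary Modeling | Postoperative GFR |
| Cohort characteristics | Preoperative creatinine/GFR, 30 days before surgery |
| Data Dictionary, Cerner extraction | Preoperative creatinine; preoperative GFR |

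Elsewhere the dictionary marks postoperative items as such: troponin is listed as preoperative and postoperative with time stamps, and vasopressors have separate postoperative rows. The missing postoperative renal row is therefore a real gap in the listing. Data sources and Data processing do provide for chart review of items not retrieved automatically, but GFR is not mentioned there.

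**2. What the plan's own missing-data rule would do.** A non-vital-sign feature missing in more than 10% is dropped: 0.10 × 750 = 75 patients. If the listed extraction were the only source, the value would be missing for everyone and the term would leave the model.

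**3. Timing.** Assume, for illustration, one postoperative GFR per patient and a troponin on each of days 0, 1 and 2. The number of the three daily outcomes that fall on a day before the GFR is then:

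| Day GFR drawn | Outcomes on earlier days |
|---|---|
| 0 | 0 of 3 |
| 1 | 1 of 3 (day 0) |
| 2 | 2 of 3 (days 0, 1) |
| 3 | 3 of 3 (days 0, 1, 2) |

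In the first three rows the GFR may also follow the troponin drawn on the same day. The collection window permits every row. The truncation rule for continuous troponin excludes none of them, because it covers vital signs only; extended to GFR, it would still cut at the final troponin and not at each day's maximum. These are counts of what is permitted, not estimates of bias.

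**4. Share of the model.** Non-intercept coefficients, with RCRI and GFR as single terms: MAP 1 + age 1 + sex 1 + emergency 1 + RCRI 1 + GFR 1 + day 2 + interaction 2 = 10. The plan's cap is 15 (750/15 = 50 patients per coefficient, the ratio it intends). Choosing a preoperative or a time-ordered postoperative GFR leaves the count at 10.

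**The case against.** The strongest defence is that a missing row in the dictionary proves little. The dictionary covers Surginet and Cerner only; chart review is a third source, and the record number is requested for that purpose. Nor is the dictionary complete: diastolic pressure, end-tidal carbon dioxide, supplementary oxygen requirement, white cell count and temperature are all used in the plan without a row. The general collection window to day 3 is not confined to vital signs, and postoperative troponin is itself a laboratory value extracted with time stamps. This stands. A reader might infer that the primary model cannot be fitted, or that no laboratory values are collected after surgery; the documents support neither.

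The binary model may also be protected. Its truncation applies to the data in general and, read plainly, would remove a day 1 GFR for a patient diagnosed on day 0. A reader might use the plan's statement that about 40% of MINS occurs on day 0 to size the problem. That figure concerns MINS, the outcome to which this rule applies, and not the continuous primary outcome. It does not measure bias.

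Finally, postoperative GFR may be deliberate. It is named consistently three times, Table 3 lists acute kidney injury separately from the preoperative kidney function in Table 1, and RCRI already contains a creatinine item. This also stands, and it argues against requiring the preoperative value. It does not supply a source or a time rule for the postoperative one.

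**Conclusion.** The point holds as a gap in specification with a risk of look-ahead in the primary model. Postoperative GFR has no stated source, and nothing requires it to precede the daily maximum troponin it predicts. It is one of 10 non-intercept coefficients and applies to all of about 750 patients.

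The consequence is conditional. If a late value is used, RMSE, R-squared and calibration could look better than the model could achieve at prediction time. A reader might conclude that performance will be inflated. The documents do not show this: they give neither the timing of GFR draws nor the strength of the relation between late GFR and troponin, so the direction is plausible and the size unknown. For the binary model, the concern falls away to the extent that its truncation is meant to include GFR.

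The conclusion assumes that no unlisted extraction rule governs this variable. It does not depend on whether postoperative is intended or a slip for preoperative; either way the sections disagree and need correction.

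**What to change.** Reconcile Other candidate features, A priori features in the primary model and Primary Modeling with Cohort characteristics and the Data Dictionary, by one of two routes.

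- **(a) If preoperative GFR was meant:** name it in all three modelling sections as the last value within 30 days before surgery. It is already in the extraction, so this is a wording change. The cost is that acute postoperative renal change is lost and the term partly overlaps the creatinine item in RCRI.
- **(b) If postoperative GFR is meant:** add time-stamped postoperative creatinine/GFR to the extraction. For each patient-day, use only the last value drawn before that day's modelled troponin, falling back to the preoperative value when none exists. The cost is a small additional data pull, and the term will mix preoperative and postoperative values, so report the share of fallbacks by day.

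Under either route, state in Data processing whether the binary model's truncation covers laboratory predictors.
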